2.5 Analysis of the primary objective

2.5.1 Primary endpoint

Event-free survival is the composite primary endpoint which is defined by the time from the date of randomization to the date of the first documented non-fatal event or death due to any cause. Non-fatal events comprise:

- Echocardiographic evidence of worsening cardiac function
- Hospitalization for congestive heart failure (CHF)
- Liver function impairment
- Liver cirrhosis
- Progression to Acute Myeloid Leukemia (AML) confirmed by bone marrow biopsy

Criteria for these events are detailed in Section 3.1.1 of the study protocol. All events which could potentially fulfill the criteria for one of the components of the endpoint (except death)

ICL670A2302

Page 22

will be reported to the Endpoint Adjudication Committee (EAC) for blinded assessment. Evaluation by the EAC is decisive for the analysis, i.e. the analysis only takes those events into account that are confirmed by the EAC.

2.5.2 Statistical hypothesis, model, and method of analysis

The sample size of 210 patients does not provide sufficient power for testing confirmatory statistical hypotheses. The analysis will therefore concentrate on estimating the treatment effect of deferasirox relative to placebo to evaluate potential event-free survival benefit and other descriptions of the survival functions.

Statistical tests will be performed in an exploratory sense only. There will be no procedures to control multiple/family-wise type-I-error probabilities regarding the different endpoints.

2.5.2.2 Estimation of survival functions for event-free survival

A graphical estimate of the survival function for each treatment group will be obtained separately by the Kaplan-Meier (KM) product-limit method as implemented in SAS PROC LIFETEST.

If available, median survival for each treatment group will be obtained by SAS PROC LIFETEST along with 2-sided 95% confidence intervals calculated using the method of (Brookmeyer and Crowley 1982).

KM estimates with 2-sided 95% confidence intervals at days 364, 728, 1092 and 1456 will be provided. The confidence intervals will be constructed using Greenwood's formula (Collett 1994) for the standard error of the Kaplan-Meier estimate.

2.5.2.3 Stratified unadjusted Cox proportional hazards regression model

For the primary analysis, an unadjusted Cox model will be used. Hazard ratio as a treatment effect measure for time to event endpoints will be derived from the *Cox proportional hazards model* using SAS procedure PHREG (with TIES=EXACT option in the MODEL statement as explained in Section 5.5.1.1). STRATA options will be used to account for variations in baseline hazards across strata.

Page 23

2.5.2.4 Statistical hypothesis test (exploratory)

A stratified log-rank test with stratification variables used in the randomization, i.e. IPSS (low or int-1) and geographical region (Asian versus non-Asian countries), will be implemented as follows: For each of the K strata, a BY statement will be used with the SAS LIFETEST procedure, while a STRATA statement including a variable for identifying the treatment group will be used to obtain the rank statistic S_k and variance $var(S_k)$ where k = 1, 2, ..., K.

The final test statistic will then be constructed as:

$$Z = [S_1 + ... + S_K] / \sqrt{[var(S_1) + ... + var(S_k)]}.$$

Under the null hypothesis, the test statistic Z is approximately normally distributed (Z^2 is approximately chi-square distributed with one degree of freedom). A one-sided (exploratory) p-value will be obtained using the Z statistic:

$$p = P(Z>z) = 1-Probnorm(z)$$

where z is the observed value of Z and Probnorm denotes the inverse of the normal cumulative distribution function.

2.5.3 Handling of missing values/censoring/discontinuations

Event-free survival

For the primary analysis of event-free survival, the following censoring rules will be applied:

- Patients who have not experienced any of the non-fatal events from the composite primary endpoint and have not stopped study participation at the time of data cut-off (end of study) will be censored - irrespective of adherence to study treatment - considering the following dates for the components and taking the earliest (minimum) of these as the censoring date:
 - Worsening of cardiac function: the last date when echocardiography results will be available
 - Hospitalization for congestive heart failure: the data cut-off date
 - Liver function impairment: the last date when laboratory values for ALT, AST and bilirubin will be available
 - Liver cirrhosis: the data cut-off date
 - Progression to AML: the data cut-off date
- Patients who have not experienced any of the non-fatal events from the composite primary endpoint, but have stopped study participation before the time of data cut-off, will be censored - irrespective of adherence to study treatment - considering the following dates for the components and taking the earliest (minimum) of these as the censoring date:
 - Worsening of cardiac function: the last date when echocardiography results will be available
 - Hospitalization for congestive heart failure: the last date when the patient will have some documented personal contact (visit or phone call) with the investigator
 - Liver function impairment: the last date when laboratory values for ALT, AST and bilirubin will be available

- Liver cirrhosis: the last date when the patient had documented personal contact (visit or phone call) with the Investigator regarding imaging, laboratory data, or biopsy results regarding cirrhosis
- Progression to AML: the last date when the patient will have some documented personal contact (visit or phone call) with the Investigator. Suspected progression to AML without confirmation by bone marrow biopsy or aspiration does not constitute an event and censoring will be applied at last contact.

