and data analysis	The Full Analysis Set (FAS) comprises all patients to whom study treatment has been assigned by randomization. According to the intention to treat principle, patients will be analyzed according to the treatment and strata they were assigned to during the randomization procedure. The FAS will be the primary analysis set for all statistical analyses of efficacy.
	• The Per Protocol Analysis Set (PPS) is a subset of the FAS and comprises all randomized patients whose first administered study medication was in accordance with the randomized assignment, and without protocol deviations regarding inclusion criteria with respect to underlying disease (e.g., low or intermediate-1 MDS according to IPSS and serum ferritin > 1000 mcg/L at screening). The PPS will be used as the secondary analysis set to perform statistical analyses of the primary efficacy endpoint.
	• The Safety Analysis Set includes all randomized patients who received at least one dose of study medication. Patients will be analyzed according to the study treatment they actually received (defined as the study medication administered first) and according to strata information recorded in the (e)CRF. All statistical analyses of safety and tolerability will be based on the Safety Analysis Set.
	Significance level:
	No confirmatory hypothesis tests will be performed. Two-sided 95% confidence intervals will be provided for estimating treatment effects of deferasirox relative to placebo. For some endpoints tests will be performed in an exploratory sense only.
	Statistical analysis methods:
	Patient demographics and baseline characteristics will be summarized by treatment group.  Primary statistical analysis method for the primary endpoint:
	For the primary analysis, the following censoring rule will be applied:
	Patients not known to have experienced any event from the composite primary endpoint
	at the time of a data cut-off will be censored - irrespective of adherence to study treatment - at the last date when there has been evidence for being event-free (details in the full protocol).
	A point estimate and two-sided confidence interval for an unadjusted hazard ratio will be obtained from a Cox proportional hazard regression model stratified for the

randomization factors IPSS and geographical region (Asian countries versus non-Asian countries).

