- f. Visit 4.01: At Week 3, Serum Creatinine is drawn and Creatinine Clearance is calculated
- g. Captured in Source Documentation only
- 1. Hemoglobin/Transfusion History: collect retrospective data for the 6 months prior to study entry
- 2. Bone marrow for cytogenetics and morphology is not required if the exam has been completed within 6 months of the screening date and the patient has been hematologically stable. Patients with a major hematological response per IWG criteria (Post Text Supplement 4) may undergo an additional bone marrow biopsy or aspiration plus bone marrow examination at the time of response if in the opinion of the investigator the information may be helpful in the management of the patient. Bone marrow examination should also be performed if the patient is suspected to have had an AML progression.
- 3. Bone marrow aspirate should include cytogenetics and morphology
- 4. Repeat bone marrow aspiration and cytogenetics, iron stains and biopsy recommended at the time of hematological improvement per IWG criteria (Post Text

	Screening		Randomization	Treatment Period												Week 372 a End of Treatment	3-day F	Evaluation c Period	Study Evaluation Completion	Survival d Follow-Up			
Visit	1	2	3 e	4 f	5	6	7	8	9	10	11	12	13	14	15	16	17	18-96	777	501	502, 503, etc.	778	701, 702, etc.
Week 	-5 1	to -	Day 1	2	4	8	12	16	20	24	28	32	36	40	44	48	52	56 368	372				

Supplement 4). Bone marrow examination should also be performed if the patient is suspected to have experienced disease progression.

- 5. ECG and ECHO will be performed at screening and approximately every 3 months (Weeks 12, 24, 36, 52, 64, 76, 88, 104, 116, 128, 140, 156, 168,180,192,208 220, 232, 244, 260, 272, 284, 296, 312, 324, 336, 348, 364, 372). Patients in the Evaluation Period will have ECGs, ECHOs performed approximately every 3 months
- 6. Chest x-ray to be performed at baseline and for any hospitalization related to CHF (pulmonary edema)
- 7. Liver Ultrasound will be performed at Screening Visit 1 and anytime during the trial if liver function impairment or liver cirrhosis is suspected. Liver biopsy will be performed if abdominal ultrasound results indicated liver damage/failure and there are no contraindications, then liver biopsy is recommended

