#### 10.4.1 Variable

The composite primary endpoint (event-free survival, a composite including death and non-fatal events related to cardiac, liver and hematological function, see Section 3.1.1) is defined as time from date of randomization to date when death (irrespective of cause) or any of the non-fatal events has been reached (whatever occurred first). Time is measured in days and is defined as date of event minus date of randomization plus 1.

Censoring for patients without information on date of event at the time of a data cut-off (for interim or final analysis) is described in Section 10.4.3.

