2.1.2.9 On-treatment assessment/event and observation periods

The overall observation period will be divided into three mutually exclusive segments:

- 1. *pre-treatment period*: before the first administration of study treatment
- 2. *on-treatment period*: from date of first administration of study treatment to 28 days after date of last actual administration of any study treatment (including start and stop date)
- 3. *post-treatment period*: starts on day 28+1 after last administration of study treatment.

Per study design, there will be two additional observation periods:

- 4. *study evaluation period:* starts on day 29 after last administration of study treatment until study evaluation completion period (visit frequency every three months)
- 5. **survival follow-up period:** starts after study evaluation completion visit until LPFV plus three years or death. If a patient declines to participate in the evaluation period, the survival follow-up period will start on day 29 after last administration of study treatment until LPFV plus three years or death (visit frequency is every 6 months).

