2.5.4 Sensitivity and supportive analyses

The two main sensitivity analyses for the primary efficacy analysis (event-free survival) will be based on the two alternative censoring rules. Otherwise, the same statistical methods will be used for the primary analysis of event-free survival. A third sensitivity analysis using the

same methodology will address the issue of partial data for the composite endpoint (i.e., a patient with some missing data but not all of the components of composite endpoints).

For the first main sensitivity analysis patients with premature discontinuation of randomized study treatment and subsequent treatment with marketed iron chelation therapy (including Exjade[®]) will be censored at the date of first administration of the subsequent iron chelation therapy.

For the second main sensitivity analysis patients with premature discontinuation of randomized study treatment (regardless of whether they were subsequently treated with marketed iron chelation therapy) will be censored at the date of last administration of randomized study treatment.

The third sensitivity analysis will employ the following censoring rules:

- If an event is documented after three or more consecutive missing biochemistry laboratory assessments (regarding results for ALT, AST, and total bilirubin), the event-free survival time of these patients will be censored at the date of the last assessment with complete information for ALT, AST, and total bilirubin.
- If an event is documented after two or more consecutive missing echocardiogram (ECHO) assessments (for left ventricular ejection fraction), the event-free survival time of these patients will be censored at the date of the last ECHO assessment.
- If an event is documented after at least three consecutive missing biochemistry laboratory assessments (ALT, AST, and total bilirubin) and at least two consecutive missing ECHO assessments simultaneously, the event-free survival will be censored at the date of the last assessment with both biochemistry laboratory and ECHO assessments completed.
- As the three other components, 'hospitalization for congestive heart failure', 'liver cirrhosis' and 'Progression to AML', i.e. assessed in unscheduled examinations, missing assessments for them cannot be determined.

Sensitivity analyses include:

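### The primary event-free-survival rule keeps survival-only follow-up for patients who die in it and discards it for those who survive, and its censoring trigger omits death

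*SAP*

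**What the plan says.** **Endpoint.** Protocol 10.4.1 runs EFS to the "date when death (irrespective of cause) or any of the non-fatal events has been reached"; SAP 2.5.1 runs it to "the date of the first documented non-fatal event or death due to any cause". Neither sets a date after which deaths stop counting.

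**Censoring.** The protocol synopsis (statistical methods) would censor "Patients not known to have experienced any event from the composite primary endpoint". SAP 2.5.3, matching protocol 10.4.3, is worded differently. Its first bullet covers "Patients who have not experienced any of the non-fatal events from the composite primary endpoint and have not stopped study participation" by the cut-off, and its second covers the same patients if they stopped earlier. Each lists a date per component, "taking the earliest (minimum) of these as the censoring date". The cardiac date is the last echocardiogram (ECHO) and the liver-function date is the last ALT, AST and bilirubin. The other three components use the cut-off or a last contact.

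**Follow-up after study drug.** Protocol Section 4 makes three-monthly evaluation visits the default but lets patient and physician decide against them. SAP 2.1.2.9 says: "If a patient declines to participate in the evaluation period, the survival follow-up period will start on day 29 after last administration". SAP 1.1 describes that phase as telephone contact every six months. In Table 7-1 its column holds only survival and chelation therapy. Note 5 says "Patients in the Evaluation Period will have ECGs, ECHOs performed approximately every 3 months" and has no counterpart for survival follow-up.

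**Alternatives (SAP 2.5.4).** The first sensitivity analysis censors at the start of another chelator. In the second, patients who stop study drug early "will be censored at the date of last administration of randomized study treatment". The third censors events that follow two or more missing ECHOs or three or more missing liver laboratory assessments.

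**The concern.** There are two faults in one rule.

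- **Trigger.** Both bullets depend on having had no non-fatal event. Read as written, they capture a patient who died without one and censor that patient. This contradicts the endpoint definition in both documents and the synopsis wording.
- **Asymmetry.** If deaths count, as clearly intended, whether a patient's survival-only time enters the analysis depends on the outcome of that time. A patient who dies contributes all of it and an event. A patient who lives contributes none.

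The trial has no confirmatory test and sets out to estimate the treatment effect (SAP 2.5.2), so the EFS hazard ratio (HR) and Kaplan-Meier curves are its main product. If leaving assessment is unrelated to prognosis, the rule pushes EFS down in both arms and moves the HR against whichever arm leaves assessment faster.

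A smaller gap is that a patient with no post-baseline ECHO or laboratory result is censored at a screening date, which gives a zero or negative time. Only the ferritin analysis (SAP 2.5.3.6) has a fallback.

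**Working it through.** **Inputs.** From the documents: 210 patients at 2:1 (SAP 3), at least 3 years of follow-up (protocol 4), and ECHO about every 3 months (Table 7-1, note 5). The plan gives no EFS rate, event target or drop-off rate, so there is no planned figure to reproduce. Assumed: death 0.125/yr, non-fatal events 0.065/yr, follow-up uniform over 3 to 8 years, 12-weekly ECHO, entry to survival-only follow-up at 0.05 to 0.4/yr, and a true HR of 1.

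**Step 1, literal trigger.** If deaths without a prior non-fatal event are censored, 4-year EFS reads exp(-0.065 x 4) = 0.77. It should read exp(-(0.125 + 0.065) x 4) = 0.47.

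**Step 2, mechanism.** Take 100 patients who enter survival-only follow-up together and are followed for 4 more years.
- Deaths: 100 x (1 - exp(-0.125 x 4)) = 39.3. Survivors: 60.7.
- True time at risk: 39.3/0.125 = 315 person-years.
- The plan drops the survivors' 60.7 x 4 = 243 person-years and keeps 72.
- Apparent death rate in that phase: 39.3/72 = 0.55/yr, against a true 0.125.

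**Step 3, simulation** (400,000 deferasirox and 200,000 placebo patients per scenario). With drop-off unrelated to prognosis:

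| Drop-off per year, deferasirox vs placebo | HR under the primary rule (true 1) |
|---|---|
| equal | 1.00 |
| 0.1 vs 0.05 | 1.05 |
| 0.2 vs 0.1 | 1.12 |
| 0.4 vs 0.2 | 1.19 |
| 0.2 vs 0.4 | 0.84 |

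With equal drop-off of 0.05, 0.1 and 0.2/yr, 4-year EFS reads 0.45, 0.43 and 0.40 against a true 0.47. Deaths in survival-only follow-up are 11 of 130 EFS events (8%) at 0.05/yr and 34 of 122 (28%) at 0.2/yr.

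If sicker patients leave sooner (gamma frailty), at 0.4 vs 0.2/yr:

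| Rule | HR, frailty variance 0.5 | HR, frailty variance 1 |
|---|---|---|
| Primary | 1.11 | 1.09 |
| Symmetric (deaths and survivors both stop at end of assessment) | 0.90 | 0.87 |
| Event-free patients censored at last contact | 0.94 | 0.96 |
| Third sensitivity analysis, ECHO limb, survival-only ECHOs counted as missing | 0.95 | 0.92 |

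The third sensitivity analysis gives 1.06 when drop-off is unrelated to prognosis.

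Varying the death and non-fatal rates from 0.10 and 0.05 to 0.15 and 0.08 per year, the primary-rule HR at 0.4 vs 0.2 is 1.15 to 1.25 with unrelated drop-off, 1.10 to 1.15 at frailty 0.5, and 1.07 to 1.09 at frailty 1. In those settings true 4-year EFS lay between the primary and last-contact results. It did not when non-fatal events predominate: with rates 0.05 and 0.15, frailty 1 and drop-off 0.2/yr, the primary rule gave 0.58 and the truth was 0.56.

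**Step 4, a higher death rate.** Protocol 1.1 cites median survival of 40 and 51 months without chelation; 40 months is ln 2/(40/12) = 0.208/yr. With these medians, non-fatal events at 0.05 or 0.10/yr (assumed) and drop-off unrelated to prognosis:
- Primary rule: HR 0.85 to 0.92 when placebo leaves faster (0.4 vs 0.2), 1.10 to 1.18 when deferasirox does.
- Across all scenarios run: symmetric rule 0.96 to 1.03, second sensitivity analysis 0.99 to 1.02, ECHO limb of the third 0.90 to 1.08.
- One-sided rejection at 210 patients (40 months, non-fatal 0.05/yr; nominal 2.5%): 2.8% with equal drop-off and 10.8% with placebo at 0.4 vs 0.2. The symmetric rule gives 3.7% in the latter case.

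**Step 5, scale.** With 120 events at 2:1, SE(log HR) = 1/sqrt(120 x 2/9) = 0.19. So ln 1.05 = 0.05 is about 0.3 SE and ln 1.19 = 0.17 is about 0.9 SE.

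**The case against.** The trigger can be called a slip. Every definition of the endpoint includes death, and few programmers would censor a patient who has reached it. That is fair, and the 0.77 describes an analysis nobody intends. A primary censoring rule should still not need to be overridden by inference.

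The stronger point is the third sensitivity analysis. It applies to any event, including death, and moves a late death back to the last assessment, where survivors already sit. At 0.4 vs 0.2/yr, with unrelated drop-off, it brings 1.19 down to about 1.06. Adding the laboratory limb with four-weekly tests brings it to about 1.02, though evaluation visits are three-monthly. This deserves credit. But it works only if tests that were never scheduled count as missing, which SAP 2.5.4 does not say, and it still counts deaths soon after assessment ends.

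Overall survival, the component curves and the chelation-censored analysis give context, but none is EFS with both groups treated alike. The second sensitivity analysis is symmetric, but only by dropping every event found in the evaluation period.

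It is also true that evaluation visits are the default, that a twofold imbalance in drop-off is assumed, and that the symmetric rule is no better than the primary one if sicker patients leave sooner. These points limit the size and argue against replacing the primary rule. They do not remove the asymmetry.

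**Conclusion.** The point holds and should be fixed. The conflict over the trigger and the asymmetry both follow from the text and need no assumption. The size does need assumptions, because the documents give no drop-off rate. With equal drop-off the HR is unbiased under no treatment effect, and only the Kaplan-Meier level suffers, by 2 to 7 points at 4 years in the runs above. With unequal drop-off unrelated to prognosis the HR moves against the arm that leaves faster, by less than one standard error in the main runs. The effect may be small if few patients decline evaluation. As planned, a reader could not tell.

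**What to change.** Keep the primary rule and make three changes.

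1. **Trigger.** In SAP 2.5.3 and protocol 10.4.3, apply both bullets to patients with no composite event, meaning neither death from any cause nor a non-fatal event confirmed by the Endpoint Adjudication Committee (EAC).
2. **Two added analyses in SAP 2.5.4**, with the same Cox and Kaplan-Meier methods, shown beside the primary result.
   - *Symmetric:* count deaths and EAC-confirmed events only up to the end of assessment, and censor everyone else there even if they die later. That date is the data cut-off, Study Evaluation Completion or, if evaluation is declined, the mandatory 28-day follow-up (protocol 6.7.5). Table 7-1 schedules no ECHO or laboratory test at that last visit, so a short unassessed interval remains, the same for both groups.
   - *Last contact:* count all deaths and EAC-confirmed events, and censor event-free patients at last contact (SAP 2.1.2.4).
   - SAP 2.3 already counts patients entering survival follow-up. Add, by arm, the EFS deaths after end of assessment. State in advance that if the three HRs differ, the EFS result depends on survival-only follow-up.
   - Present neither addition as the correct answer. The symmetric rule is biased the other way if sicker patients leave sooner, and the last-contact rule misses later non-fatal events.
   - Say whether unscheduled tests in survival-only follow-up count as missing in the third sensitivity analysis.
3. **Fallback.** Set censoring to Day 1 when there is no post-baseline ECHO or laboratory result. This has almost no numerical effect.

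The cost is a wording change in both documents and two reruns of existing programs on dates already collected. The downsides are fewer events in the symmetric analysis and three EFS estimates to present.

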#### 10.4.3 Handling of missing values/censoring/discontinuations

#### **Event-free survival**

For the primary analysis of event-free survival,

- Patients who have not experienced any of the non-fatal events from the composite primary
  endpoint and have not stopped study participation at the time of data cut-off (end of study)
  will be censored irrespective of adherence to study treatment considering the following
  dates for the components and taking the earliest (minimum) of these as the censoring date:
  - Worsening of cardiac function: the last date when echocardiography results were available,
  - Hospitalization for congestive heart failure: the data cut-off date,
  - Liver function impairment: the last date when laboratory values for ALT, AST and bilirubin were available,
  - Liver cirrhosis: the data cut-off date,
  - Progression to AML: the data cut-off date;
- Patients who have not experienced any of the non-fatal events from the composite primary
  endpoint but have stopped study participation before the time of data cut-off will be
  censored irrespective of adherence to study treatment considering the following dates
  for the components and taking the earliest (minimum) of these as the censoring date:
  - Worsening of cardiac function: the last date when echocardiography results were available,
  - Hospitalization for congestive heart failure: the last date when the patient had some documented personal contact (visit or phone call) with the investigator,
  - Liver function impairment: the last date when laboratory values for ALT, AST and bilirubin were available,
  - Liver cirrhosis: the last date when the patient had some documented personal contact (visit or phone call) with the investigator,

Progression to AML: the last date when the patient had some documented personal contact (visit or phone call) with the investigator. Suspected progression to AML without confirmation by bone marrow biopsy or aspiration does not constitute an event and censoring will be applied as described.

For the first main sensitivity analysis described in Section 10.4.4, patients with premature discontinuation of randomized study treatment and subsequent treatment with marketed iron chelation therapy (including Exjade®) will be censored at the date of first administration of the subsequent iron chelation therapy.

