2.5.3.4 Liver cirrhosis

For the analysis of liver cirrhosis, patients who have not experienced liver cirrhosis will be censored at the last contact date.

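### SAP 2.5.3 narrows the cirrhosis censoring date for event-free patients who leave the study early, against the protocol and SAP 2.5.3.4; depending on how the clause is read, the primary analysis loses almost nothing or all follow-up of patients never worked up

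*SAP*

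**What the plan says.** Protocol 10.4.3 and SAP 2.5.3 use the same structure for the primary EFS analysis. Each component of the composite has its own last-known-free date, and the plan censors by "taking the earliest (minimum) of these as the censoring date".

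For event-free patients still participating at cut-off, the SAP entry is "Liver cirrhosis: the data cut-off date", as in the protocol. The documents differ only for patients who are event-free "but have stopped study participation before the time of data cut-off":

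- Protocol 10.4.3: "Liver cirrhosis: the last date when the patient had some documented personal contact (visit or phone call) with the investigator".
- SAP 2.5.3: the contact with the investigator must be one "regarding imaging, laboratory data, or biopsy results regarding cirrhosis".

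In the same SAP list, the heart-failure and AML entries keep the unrestricted contact wording; only cirrhosis was narrowed. For the separate analysis of the cirrhosis component, SAP 2.5.3.4 says that "patients who have not experienced liver cirrhosis will be censored at the last contact date". SAP Section 4 lists one departure from the protocol, the redefinition of newly occurring cytopenias.

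On when liver imaging is done, the protocol's Table 7-1, footnote 7, says: "Liver Ultrasound will be performed at Screening Visit 1 and anytime during the trial if liver function impairment or liver cirrhosis is suspected". Biopsy is recommended if the ultrasound shows damage. ALT, AST and total bilirubin are measured monthly.

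**The concern.** Because the rule takes a minimum, one early component date fixes the EFS censoring date whatever the other four say. After screening, ultrasound and biopsy depend on suspicion, and both documents describe cirrhosis as assessed in unscheduled examinations. Read literally as contact about a cirrhosis work-up, the clause gives a patient who was never suspected either no date at all or the date of the screening ultrasound, before randomization. The SAP supplies a randomization-date fallback for serum ferritin (2.5.3.6) but none for EFS.

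Patients reset in this way would drop out of the risk set at the start, while patients with events keep their full time. That lowers the Kaplan-Meier curves in both arms and distorts the HR when leaving the study differs by arm. The plan makes estimation of the treatment effect its main product, so these estimates matter although testing is exploratory. A primary censoring date that depends on how a programmer reads one clause is not pre-specified.

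**Working it through.** The plan has no figure of its own to reproduce: the 210 patients rest on feasibility, and no event or drop-out rate is given. The check is therefore a reading of the clause, then a calculation under assumed rates.

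**1. What each reading does**

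| Reading of the SAP clause | Cirrhosis date for a patient never suspected | Effect on EFS censoring |
|---|---|---|
| Routine liver tests count as laboratory data | About the last ALT/AST/bilirubin date, already in the minimum | Almost none |
| Only a work-up counts; a missing date is skipped in the minimum | None used | None |
| Only a work-up counts; screening ultrasound used, or missing set to Day 1 | At or before Day 1 | All follow-up lost |
| Protocol wording | Last contact, which cannot precede the last ECHO or liver test | None |

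**2. Hand check of the last-reset case**

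Assumptions: exponential times; placebo event hazard λ = 0.20/year; true HR 0.70, so deferasirox λ = 0.14; drop-out from the study γ = 0.25 (deferasirox) and 0.15 (placebo) per year; A = 5 years of follow-up for everyone.

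Share leaving event-free: L = γ/(λ+γ) × (1 − exp(−(λ+γ)A)).

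- Placebo: 0.15/0.35 × (1 − exp(−1.75)) = 0.429 × 0.826 = 0.354.
- Deferasirox: 0.25/0.39 × (1 − exp(−1.95)) = 0.641 × 0.858 = 0.550.

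If all leavers are reset to Day 1, a share 1 − L remains at risk but every event is kept, so the apparent hazard just after Day 1 is λ/(1 − L).

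- Placebo: 0.20/0.646 = 0.310. Deferasirox: 0.14/0.450 = 0.311. Ratio 1.00 instead of 0.70.

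By year 5 no leavers remain to be removed and the ratio returns to 0.70. A Cox model averages over this path.

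With the drop-out rates exchanged: placebo L = 0.25/0.45 × (1 − exp(−2.25)) = 0.497, hazard 0.20/0.503 = 0.398; deferasirox L = 0.15/0.29 × (1 − exp(−1.45)) = 0.396, hazard 0.14/0.604 = 0.232. Initial ratio 0.58.

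**3. Simulation (exponential times, staggered follow-up of at least 3 years, unstratified Cox model)**

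| Drop-out/year, deferasirox vs placebo | Event-free leavers reset | True HR 0.70 reads |
|---|---|---|
| 0.25 vs 0.15 | none | 0.70 |
| 0.25 vs 0.15 | half | about 0.78 |
| 0.25 vs 0.15 | all | about 0.90 |
| 0.12 vs 0.10 | half | about 0.72 |
| 0.12 vs 0.10 | all | about 0.75 |
| 0.15 vs 0.25 | all | about 0.57 to 0.62 |

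The first five rows use a placebo hazard of 0.20/year; the last covers 0.15 to 0.25/year. Over hazards of 0.15 to 0.25 and drop-out of 0.15 to 0.25 per year:

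- Resetting all leavers removes 26 to 38% of EFS person-time; resetting half removes 13 to 19%.
- With hazard 0.25/year, true 3-year placebo EFS of exp(−0.75) = 0.472 reads 0.28 to 0.35 when all are reset.
- With equal drop-out, a true HR of 1.0 stays at 1.00. With 0.25 vs 0.15 and all reset, it reads 1.19 to 1.23; with the arms exchanged, 0.83.
- With the protocol rule, bounded by the last 12-weekly ECHO, the same simulations return HRs of 0.68 to 0.72 for a true 0.70.

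**The case against.** A reader might infer that every unsuspected patient who leaves event-free is sent back to the screening ultrasound and contributes no time. The documents do not establish that. The clause also names laboratory data, and liver biochemistry runs monthly on treatment and at later evaluation visits, so a fair reader may count those visits. Patients still participating at cut-off are credited to that date with no work-up required, which argues against an intent to penalize leavers. Even on the narrow reading, a missing date need not become Day 1. This stands: the outcome is undetermined rather than plainly destructive.

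It does not make the wording safe. The cirrhosis criteria are clinical signs, ultrasound or biopsy, with no laboratory test, and ALT/AST/bilirubin already have their own censoring entry. On the benign reading the added words do nothing; on the other they remove follow-up.

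A reader might also infer that GI and renal toxicity makes unequal drop-out likely. That does not follow. The rule covers leaving the study, irrespective of adherence. Patients who stop the drug continue in 3-monthly evaluation unless they decline it, and no document gives a rate of leaving in either arm.

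Lastly, the second main sensitivity analysis censors premature discontinuers at last dose and does not use the cirrhosis date, so a gross artefact should show as a discrepancy. That helps detection, but leaves the primary estimate wrong.

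**Conclusion.** The inconsistency holds on the text: SAP 2.5.3 departs from protocol 10.4.3 and from SAP 2.5.3.4, within a minimum rule for the primary endpoint, and does not declare the change. It affects only event-free patients who stopped participation before cut-off.

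Its size runs from practically none to substantial, depending on interpretation and programming. The upper end needs three things together: the narrow reading, a Day 1 or screening date for patients never worked up, and many patients leaving the study. Distortion of a null HR further needs unequal leaving between arms. All rates used here are assumptions. Confidence is high that the texts conflict and moderate about any effect on the result.

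**What to change.** In SAP 2.5.3, for patients who stopped before cut-off, replace the cirrhosis entry with the last contact date, as in protocol 10.4.3 and SAP 2.5.3.4. Add that the EFS censoring date is never earlier than the randomization date (Day 1). If the narrower rule is intended, declare and justify it in SAP Section 4, define which contacts qualify, and give a fallback when there is none.

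The cost is one line of SAP text and a programming check that no EFS time falls below one day. No new data are needed. It should be settled before treatment codes are opened for analysis.
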